6. FUTURE DIRECTIONS

This project tests the hypothesis that CSF pT181/T181 is decreased with lemborexant, a DORA, compared to placebo. The proposed study may suggest innovative AD prevention and treatment approaches that involve sleep therapies such as DORAs in older individuals with poor sleep quality. If successful, future studies will include an interventional trial to prevent amyloidosis (or slow amyloid growth) and tauopathy in those identified by clinical criteria. Such a prevention trial could dramatically impact the incidence and prevalence of AD.

SUPPLEMENTAL MATERIAL

Supplementary Figure 1: A β labeling curves for stable isotope labeling kinetics (SILK) for A β 38 (A), A β 40 (B), and A β 42 (C). 800 mg of 13C6-leucine is infused over 10 minutes at 20:00 (t=0) in participants treated with placebo (N=11), suvorexant 10 mg (N=11), and suvorexant 20 mg (N=6). Note, this data has not been normalized to the plasma free leucine concentration and A β kinetics cannot be determined. This data is presented to demonstrate feasibility. Standard error bars are shown. Unpublished data.

7. STUDY POPULATION AND ENROLLMENT

7.1 Justification for human subject involvement:

Alzheimer Disease (AD) is a current and growing public health problem characterized by progressive cognitive impairment resulting in dementia. AD is estimated to afflict millions of people in the coming decades. Multiple lines of evidence suggest a role for sleep disturbances in the development of AD. Further, there is evidence in mice that improving sleep parameters such as sleep efficiency (i.e. sleep quality) may prevent the initial pathological changes seen in the brain with AD. These findings need to be replicated in humans if sleep interventions are to be deployed to prevent or delay AD. In this study, I propose to translate the findings to humans that improving sleep efficiency has similar effects

Lemborexant 25 mg Overview
[name], Washington University

as in mice. The specific objective of this study is to translate basic science findings to humans for the long-term improvement in human health, therefore the proposed study must be carried out in human subjects.

7.2 Subject population characteristics:

The goal is to enroll healthy, cognitively normal amyloid-positive adults 60-80 years old with no medical comorbidities that would affect the risk of AD and with no conditions, medications, or substance use that may affect outcome measures or contraindicate study procedures (e.g. cerebrospinal fluid (CSF) amyloid- β (A β) levels obtained by lumbar catheter). Participants will be recruited from the Volunteers for Health registry of >10,000 research study volunteers maintained at Washington University, the ADRC, as well as an ongoing study of a plasma A β test (SEABIRD, PI: [name]). Individuals from both sexes and any race or ethnicity will be included. Minors will not be included because AD does not occur in individuals <18 years old, even if predisposed to develop AD through an autosomal dominant mutation. Further, it is not known if the diurnal A β pattern is present in children. The relevance of determining if sleep alters A β in children to the pathogenesis of a neurodegenerative disorder that will potentially develop decades later is also unknown at this time. As a result, we will not include any children in this study.

7.3 Eligibility criteria:

7.3.1 Inclusion criteria:

- Age 60-80 years
- Any sex
- Any race/ethnicity
- Mini-Mental Status Examination score (MMSE) ≥ 27
- Positive plasma A β test (i.e., amyloid-positive)
- Pittsburgh Sleep Quality Index >5

7.3.2 Exclusion criteria:

- Cognitive impairment as determined by history of MMSE < 27
- Inability to speak or understand English
- Any sleep disorders other than insomnia
 - No history of moderate-to-severe sleep-disordered breathing and STOP-Bang score > 5
 - History or reported symptoms suggestive of restless legs syndrome, narcolepsy or other sleep disorders
 - No more than mild sleep apnea (AHI <16) on PSG
- Sleep schedule outside the range of bedtime 22:00-midnight
- Contraindication to lumbar catheter (anticoagulants; bleeding disorder; allergy to lidocaine or disinfectant; prior central nervous system or lower back surgery)
- Cardiovascular disease requiring medication except for controlled hypertension (PI discretion)
- Stroke
- Hepatic or renal impairment

Lemborexant 25 mg Overview
[name], Washington University

- Pulmonary disease (PI discretion)
- Type 1 diabetes
- HIV or AIDS
- Neurologic or psychiatric disorder requiring medication (PI discretion)
- Suicidal ideations
- Alcohol, tobacco or marijuana use (PI discretion)
- Use of sedating medications (PI discretion)
- Inability to get out of bed independently
- In the opinion of the investigator, the participant should be excluded due to an abnormal physical examination.
- Current pregnancy
- Body Mass Index >35
- History of migraines (PI discretion)
- History of drug abuse in the last 6 months
- History or presence of any clinically significant medical condition, behavioral or psychiatric disorder (including suicidal ideation), or surgical history based on medical record or patient report that could affect the safety of the subject or interfere with study assessments or in the judgment of the PI participant is not a good candidate.
- Urinary or fecal incontinence
- Concurrently enrolled in another trial of an investigational drug or device

We will enroll up to 30 participants to complete the study. **Participants will receive either placebo or lemborexant 25 mg, a dual orexin receptor antagonist. Lemborexant is approved by the Food and Drug Administration (FDA) for the treatment of insomnia (approved doses 5-10 mg).** Lemborexant 25 mg will be used in this study to see if there is an effect on CSF pT181/T181 and A β . The use in this study will be considered investigational and is not approved by the Food and Drug Administration (FDA).

Participants that screen fail may be invited back to rescreen at a later date.

Sampling plan and justification:

- Power calculations are shown in “C3. Power Calculation” portion of the research plan above. Due to concerns about recruitment if participants have to repeat the study, the study power calculation is based on each participant completing the study once without repeating.
- Children will be excluded and age range will be limited to 60-80, as detailed in the previous section “Subject population characteristics”.

Vulnerable populations: We will not enroll participants from vulnerable populations.

Assignment to a study group: Participants will be randomized to receive placebo or lemborexant 25 mg at the Clinical Translational Research Unit (CTRU) admission. We will randomize 8 participants to receive 25 mg of lemborexant for 2 nights and 4 participants to receive placebo for two nights. After an interim analysis for safety and futility, a decision will be made to either: 1) continue the study with lemborexant 25 mg, 2) continue the study

Eisai Inc.

Version 3.0 2023-06-08

CONFIDENTIAL

Page 22 of 58

Lemborexant 25 mg Overview

[name], Washington University

with a lower dose of lemborexant, or 3) stop the study. If the study is continued, then 12 participants will be randomized to lemborexant and 6 participants will be randomized to placebo. In addition to being a FDA approved drug for the treatment of insomnia, lemborexant is also a drug with the same mechanism of action as was used in experiments to decrease A β with sleep in mice, therefore this will be a direct translation of this finding. The drug's mechanism of action is to block orexin-A and orexin-B receptors. The orexin neuropeptide acts in the brain to promote wakefulness. Through antagonism of this system, sleep is induced.

Collaborating sites: None

7.4 Description of Study Visits:

At all study visits, safety assessments will consist of monitoring and recording all adverse events (AEs) at each visit.

7.4.1 Visit 1:

Participants must provide informed consent prior to any study related assessments take place. Screening assessments include review of demographics, medical history, and medications. Vital signs and a physical and neurological exam are performed. Blood is collected for the amyloid blood test and APOE testing (APOE processing will not occur until later in the screening period and may not be processed at all should participants screen fail) and questionnaires are administered. If the participant was referred by SEABIRD, the amyloid blood test may not need to be repeated. However, if the participant was referred by the ADRC, the amyloid blood test will be repeated.

Additional safety assessment at this visit include an electrocardiogram (ECG), routine blood tests, and administration of the Columbia Suicide Rating Scale (CSSRS).

Participants will be sent home with a sleep log to complete for two weeks.

7.4.2 Visit 2:

Participants will undergo polysomnography (attended sleep study) at the Washington University Sleep Medicine Center for sleep apnea screening. Participants will have the option to have the sleep study results added to their medical record. All participants will receive a generic letter stating if the results were normal or abnormal. Participants with abnormal results will be encouraged to follow up with their primary care physician.

7.4.3 Visit 3:

This visit will occur one week prior to the Clinical Translational Research Unit (CTRU) admission. Eligibility criteria, and changes to medical conditions or medications will be reviewed. Weight will be measured, blood will be collected for a coagulation panel and participants will be sent home with a sleep log.

Lemborexant 25 mg Overview [name], Washington University

7.4.4 Visit 4:

Participants will be admitted to the Clinical Translational Research Unit (CTRU) for a 3-night stay. Questionnaires and psychomotor vigilance testing (PVT) will be administered at admission and discharge.

Throughout the CTRU admission, participants will be monitored with a full 10-20 EEG montage as well as bilateral EOG and chin EMG to stage sleep. EEG monitoring will occur throughout the CTRU stay while CSF and blood sampling occur.

The participant's habitual bedtime is based on the sleep log completed after visit 1. The leucine infusion (T=0) will begin approximately one hour prior to the habitual bedtime (~21:00-23:00).

Lemborexant 25mg or placebo will be administered ~ the participant's habitual bedtime on day 1 (hour 1) and day 2 (hour 25), and the lights will be turned off to allow for sleep.

Blood and CSF samples will be collected over 48 hours as specified below. CSF safety labs will be collected at the end of the sampling period. The nursing staff will monitor participants throughout the stay, and all food and water intake will be recorded during the sampling period.

Participants stay 8-12 hours after the study is completed for observation to monitor for adverse events. Participants will contact the study team after discharge if they develop any physical complaints. In addition, the physician or a member of the research staff will contact participants by phone 24 and 48 hours after discharge.

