A maximum of 30 participants will be recruited for this study and will be randomized in a 2:1 (treatment:placebo) ratio with lemborexant 25 mg (N=20) and placebo (N=10). Our preliminary data was used to estimate the effect size between the placebo arm and suvorexant 20 mg arm. Effect sizes were calculated based on two-sided independent two-sample *t* test with type I error of 0.05 and 80% power. G*power 3.1 was used to calculate effect sizes and

Table 4. Power Analysis and Change from Baseline Detected with Different Sample Sizes

	pT181/T181 [norm t=0; average t=14-18]	pS202/S202 [norm t=0; average t=36]	A β 42 [norm average t=0- 6; average t=22-26]
Placebo Group Mean (SD)	1.56 (1.41)	-2.83 (1.37)	123.97 (13.16)
Suvorexant 20 mg Group Mean (SD)	-1.09 (2.20)	-4.52 (3.01)	110.21 (16.66)
Effect Size of Suvorexant 20 mg Compared to Placebo	1.43	0.72	0.92
Power (10 participants/group)	86%	33%	50%
Power (15 participants/group)	95%	47%	65%
Power (20 participants/group)	99%	60%	80%

Lemborexant 25 mg Overview

[name], Washington University

perform the power calculation. Table 4 shows the power analysis for CSF pT181/T181, pS202/S202, and A β 42.

Effect sizes were calculated based on the preliminary data in Figures 2-4 and assume equal intervention groups. For CSF pT181/T181, the average of hours 14-18 in Figure 3C was used to determine means, standard deviations, and effect size. For CSF pS202/S202, the average of hour 36 in Figure 4C was used to determine means, standard deviations, and effect size. For CSF A β 42, the average of hours 22-26 in Figure 2C was used to determine means, standard deviations, and effect size. Table 4 shows the power to detect these effect sizes with 10 participants/group, 15 participants/group, and 20 participants/group. Note, CSF A β 42 may increase in amyloid-positive participants with amyloid plaque accumulation is decreased.

3.4 Interim Analysis:

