After 12 participants have completed the study (placebo N=4; lemborexant N=8), an interim analysis will be performed for efficacy to see if there is a significant difference in CSF pT181/T181 between lemborexant 25 mg and placebo groups. If there is a statistically significant ($p<0.05$) or trend towards statistically significant ($p<0.1$) reduction in the primary outcome (CSF pT181/T181 ratio) or secondary outcome (CSF amyloid-beta), then the study may be continued at lemborexant 25 mg. If there is not a trend towards a statistically significant ($p>0.1$) reduction in the primary outcome (CSF pT181/T181 ratio) or secondary outcome (CSF amyloid-beta), or power analysis suggests that statistical significance will not be achieved by the fully enrolled study, then the study will be terminated.

3.5 Data Analysis Plan:

For each participant, AD biomarkers (A β 38, A β 40, A β 42, T181, S202, T217, pT181, pS202, pT217) will be normalized to the average of the first 6 hours ($t=0-6$, 20:00-02:00) before changes from the intervention will be seen in CSF. We will also normalize to the hour 0 concentration. Phosphorylated tau ratios (pT181/T181, pS202/S202, pT217/T217) will be normalized to the first time point (hour 0). The trajectory of changes from these baselines over time will then be plotted by treatment arms to examine whether the change in concentrations or ratios is linear. If the linearity assumption is valid, (linear mixed effects) LME models with random intercept and slope, similar to our previous work^{3, 5}, will be used for analysis, otherwise mixed model for repeated measure (MMRM) will be used. Fixed effect in the model will include treatment group, time and their interaction. Baseline will be included as a covariate. The normality assumption will be examined using residual plot and appropriate transformation (e.g., log) will be considered. Unstructured covariance matrix will be used and if there is convergence issue, various other covariance matrix structure (e.g., compound symmetry, First-order Autoregressive) will be compared and the best fit structure will be selected for final analysis based on Akaike information criterion (AIC).

Lemborexant 25 mg Overview
[name], Washington University

3.6 Study Outline and Timeline:

[figure not shown]

Figure 6 shows an overview of the study design with a habitual bedtime of 22:00. Table 5 shows the study timeline. We anticipate that this study will take 2 years to complete.

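### Arm totals are fixed within two enrolment stages (8:4, then 12:6), but the section 3.5 model has no stage term; a between-stage difference in post-baseline change would cost some precision, without bias

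*Combined protocol and SAP*

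**What the plan says.** The paragraph on assignment to a study group (under section 7.3.2) begins: "We will randomize 8 participants to receive 25 mg of lemborexant for 2 nights and 4 participants to receive placebo". If the study goes on after the interim, "then 12 participants will be randomized to lemborexant and 6 participants will be randomized to placebo". Section 3.4 agrees on the first set: "After 12 participants have completed the study (placebo N=4; lemborexant N=8), an interim analysis will be performed". The two sets add up to the 20:10 of section 3.3. The protocol does not call them stages or strata and describes no blocking inside them; "stage" is my word for first 12 versus last 18.

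Section 3.5 gives the model: "Fixed effect in the model will include treatment group, time and their interaction", with baseline as a covariate. It is a linear mixed model with random intercept and slope if trajectories are linear, and an MMRM otherwise. Each phosphorylation ratio is expressed relative to the participant's own hour 0. Concentrations are expressed relative to the mean of hours 0 to 6, and also to hour 0. Section 4 adds covariates such as sex, race and age, plus others it does not name. Stage is not mentioned.

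**The concern.** When arm totals are fixed within groups, the analysis normally conditions on those groups. If it does not, any outcome difference between them sits in the residual although the design has already balanced it across arms. Standard errors are then too wide and tests conservative.

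A difference between stages is plausible here, though not documented. The interim tests CSF pT181/T181, so first-stage samples must be assayed before the decision to continue. Recruitment draws on a community registry, the ADRC and SEABIRD at about one participant a month (section 5), so case mix could drift. What is at stake is some power, mainly for the secondary outcomes, which have little to spare at 20:10.

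**Working it through.** **1. Reproduce Table 4.** Section 3.3 uses a "two-sided independent two-sample *t* test with type I error of 0.05" and says its effect sizes "assume equal intervention groups". For pT181/T181, d = (1.56 + 1.09) / √((1.41² + 2.20²)/2) = 2.65/1.848 = 1.43, as stated. Noncentral-t power at 10, 15 and 20 per group is 85.6%, 96.6% and 99.3%, against 86%, 95% and 99% in the table. The method reproduces the primary row to within 2 points.

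**2. Planned 20:10, no stage difference.** Power is about 94.5% (pT181/T181, d = 1.43), 63% (Aβ42, d = 0.92) and 43% (pS202/S202, d = 0.72).

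**3. Bias.** 8/12 = 12/18 = 2/3, so stage and treatment are orthogonal. With one value per person and no missing data, the treatment estimate is identical with and without a stage term. Only its standard error changes.

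**4. Standard error.** Let s be the between-stage difference in within-arm SDs of the analysed outcome. Stage shares are 12/30 = 0.4 and 18/30 = 0.6, and 0.4 × 0.6 = 0.24. Ignoring stage adds 30 × 0.24s² to a residual sum of squares on 28 degrees of freedom, so the SE is multiplied by √(1 + 0.24s² × 30/28).
- s = 0.25: 1.008
- s = 0.5: 1.032
- s = 1.0: 1.121

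**5. Size and power.** Results from 100,000 simulated trials per scenario, 8:4 then 12:6, one value per person, all trials run to 30:

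| s | Size without stage | pT181/T181 without / with | Aβ42 without / with | pS202/S202 without / with |
|---|---|---|---|---|
| 0 | 5.0% | 94.5 / 94.5% | 63.1 / 63.0% | 43.4 / 43.3% |
| 0.5 | 4.4% | 93.8 / 94.5% | 60.9 / 63.1% | 40.8 / 43.1% |
| 1.0 | 2.9% | 91.2 / 94.5% | 53.6 / 62.8% | 34.4 / 43.2% |

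With the stage term, size is 5.0% in all three rows.

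**6. Which differences count.** A second simulation (20,000 trials, 25 sampling times, illustrative variance components) separated level from slope.
- A 1 SD level shift present from hour 0 left the SE of the slope contrast at 0.389 and that of the change from hour 0 at 0.445, with or without a stage term.
- A 1 SD shift in slope raised the slope SE to 0.435, against 0.388 with stage fitted. Power was 61% against 69%.

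**7. Additive assay offset.** If normalisation subtracts baseline, the offset cancels. If it divides, an offset of fraction f of baseline turns a change c into c/(1+f), so the mean moves by m × f/(1+f). I take Table 4 as percent change and weight arms 2:1:
- pT181/T181: m = (2 × −1.09 + 1.56)/3 = −0.21, SD 1.85
- Aβ42: m = (2 × 10.21 + 23.97)/3 = 14.80, SD 15.01
- pS202/S202: m = (2 × −4.52 − 2.83)/3 = −3.96, SD 2.34

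For f = 0.10 the shifts are 0.01, 0.09 and 0.15 SD. For f = 0.50 they are 0.04, 0.33 and 0.56 SD.

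**8. Interim stop.** I required p < 0.1 on pT181/T181 at 8:4 before continuing. This is stricter than section 3.4, which also accepts a secondary outcome. The stage term's gain in the chance of continuing and then reaching p < 0.05 on the primary is about 1.1 points at s = 1.0 and 0.2 to 0.3 at s = 0.5.

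**The case against.** The strongest reply is that the planned analysis already handles the obvious threat. Each participant is their own reference and baseline is a covariate, so a reader who infers that every shift between stages costs power goes too far. Step 6 shows that a level shift does not, and step 7 shows that an additive assay offset barely touches the primary outcome. This stands and limits the point to post-baseline change.

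Next, nothing in the documents shows that such a difference exists. There is one site and one set of criteria. Recruitment sources are not said to vary by stage, and nothing says whether assay runs split after participant 12 or whether samples are re-run together. This also stands: the shift size is purely assumed.

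A third reply concerns the remedy. A stage main effect is constant within a person and does not enter a slope contrast, so stage-by-time is needed. In an MMRM with 24 post-baseline times that means many parameters. The first half is right. The parameter count is not decisive, because with complete data each contrast still loses only about one between-person degree of freedom. Section 8.1.1 expects some catheters to fail, so with missing samples this is approximate.

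Finally, section 4 leaves room for unnamed covariates. It does not commit to stage, while section 16 promises pre-specified comparisons.

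**Conclusion.** The point holds in a limited form. The model omits a factor within which the arm totals are fixed, and the only exposure is a between-stage difference in post-baseline change or slope. At an assumed 0.5 SD the loss is under 1 point of power for the primary outcome and about 2 points for Aβ42 and pS202/S202. At 1 SD it is about 3 and 9 points, and that case is an upper illustration, not an expectation. These figures use Table 4's suvorexant effects, one value per person, no missing data and no stopping at the interim; allowing for stopping shrinks the gain for the primary outcome.

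A reader might infer that the treatment effect is biased or confounded with calendar time. The documents do not support that, because both stages are 2:1 and omitting stage errs on the conservative side. Selection on a favourable interim result is a different matter, which a stage term neither causes nor cures.

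**What to change.** Add to section 3.5, in substance: enrolment stage (first 12 versus last 18), matching the two-stage randomisation, is a fixed effect in all primary and secondary models; where the contrast is treatment-by-time or an arm difference at particular hours, stage-by-time is included as well.

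No new data are needed. The cost is about one between-person degree of freedom per contrast, or about 0.1 point of power if the stages do not differ. Naming it now also keeps stage adjustment from becoming a choice made after the interim data are seen.

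Separately, section 3.4 provides only for continuing at the same dose or terminating, while the assignment paragraph under 7.3.2 also allows the dose to change after the interim. These passages must be reconciled. A stage term does not resolve that, because the stages would then differ in treatment.
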